9.3.3.5. Diabetic Ketoacidosis

During the clinical trial period, potential DKA will be monitored by the measurement of urinary ketones and assessment for signs or symptoms of acidosis at each clinic visit. Clinical presentations or laboratory values that suggest acidosis are to be documented in the DKA CRF. A data package of a suspected DKA case will be provided to the blinded DKA adjudicator. A DKA adjudication form will be completed and event assigned to one of the 5 categories by the independent DKA adjudicator based on clinical data and specified case definitions as outlined below.

Table 7. DKA Case Definitions

Case Term	Case Definitions
Confirmed DKA	
 an episode consisting of symptoms of DKA with ketonuria or ketonemia, AND with one or more biochemical findings of acidosis, which responds to fluid replenishment and, if needed, insulin
Probable DKA	
 an episode consisting of moderate or severe symptoms of DKA, which responds to fluid replenishment and, if needed, insulin OR an episode consisting of moderate or severe symptoms of DKA, moderate or large ketonuria and/or ketonemia without one or more biochemical findings of acidosis, which responds to fluid replenishment and/or insulin
Possible DKA	
 an episode consisting of mild to moderate symptoms of DKA, ketosis not measured or ketonuria moderate or less, condition self-managed, resolves with or without change in diabetic medications; OR an episode of 4+ or greater (40 mg/dL or greater) ketonuria with mild symptoms of DKA; OR an episode of 5+ or greater (80 mg/dL or greater) ketonuria without symptoms of DKA
Unlikely DKA	
 an episode consisting of mild symptoms of DKA with urine ketones measured small or negative; or a measurement of moderate (2+) or less ketonuria without symptoms
Indeterminate DKA	
 mild to moderate symptoms of DKA without measurement of ketosis; self-managed and/or self-resolving

Additional potential DKA cases may be identified by the adjudicator when reviewing serious adverse event listing or programmatically based on AEs of special interest preferred term list which includes relevant acidosis terms in the MedDRA dictionary. A data package will be generated and submitted to the DKA adjudicator prior to study completion and treatment assignment unblinded. All suspected DKA will be presented in a by-subject listing. Events adjudicated to be “Confirmed DKA” and “Probable DKA” will be summarized in the AEs of special interest table.

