6.10.11 Diabetic Ketoacidosis (DKA)

DKA is a serious, acute complication of diabetes and can be life-threatening. Subjects will be educated on the signs and symptoms of DKA and are required to call the study site and seek treatment should such signs or symptoms occur.

During the clinical trial period, potential DKA events will be monitored by the routine measurement of urinary ketones and assessment for signs or symptoms of acidosis at each clinic visit. Clinical presentations, such as difficulty breathing, abdominal pain, nausea, vomiting, lethargy, or a fruity smell on the breath, or laboratory values that suggest clinically-significant acidosis should be documented; treatment of DKA should be provided as appropriate.

If ongoing symptoms or signs suggest a possible DKA, the investigator should perform relevant laboratory testing while directing appropriate medical care for the subject. If DKA is suspected, regardless of the blood glucose level, the following assessments should be done immediately: physical exam and serum glucose, bicarbonate, electrolytes, and serum ketones measured STAT at a local laboratory. If ketoacidosis is likely, investigational product administration should be discontinued and immediate appropriate medical therapy, including insulin and volume repletion, should be initiated. A glucose infusion may be provided if necessary to avoid hypoglycemia during insulin therapy. Insulin treatment should continue until resolution of the ketoacidosis and stabilization of the subject's clinical condition. Investigational product administration may be resumed following stabilization of the subject's condition. Investigator should collect the data necessary for the completion of the DKA CRF.

If symptoms suggestive of DKA may have occurred but are not ongoing, the investigator should review available data in order to complete the DKA CRF. The investigator may also perform laboratory assessment using local resources if necessary for clinical care.

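### SAP Table 7 requires response to treatment for Confirmed and Probable DKA, so a severe, biochemically documented ketoacidosis that ends in death without response fits no category

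*Combined protocol and SAP*

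**What the plan says.** SAP 9.3.3.5 sends a data package for each suspected case to a blinded adjudicator, with the "event assigned to one of the 5 categories by the independent DKA adjudicator" on the basis of clinical data and the definitions in Table 7. Response to treatment appears in three places in that table:

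- Confirmed DKA: symptoms, ketonuria or ketonemia, and "one or more biochemical findings of acidosis, which responds to fluid replenishment and, if needed, insulin".
- Probable DKA, first branch: "an episode consisting of moderate or severe symptoms of DKA, which responds to fluid replenishment and, if needed, insulin".
- Probable DKA, second branch: moderate or severe symptoms with moderate or large ketonuria and/or ketonemia, "without one or more biochemical findings of acidosis, which responds to fluid replenishment and/or insulin".

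The other categories are for milder pictures. Possible DKA has three branches. One covers mild to moderate symptoms with "ketosis not measured or ketonuria moderate or less, condition self-managed, resolves with or without change in diabetic medications". Another is for 4+ ketonuria where symptoms are only mild, and the last is for 5+ ketonuria with no symptoms. Unlikely needs mild or no symptoms with low ketones. Indeterminate needs mild to moderate symptoms, unmeasured ketosis and a self-managed or self-resolving course.

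SAP 9.3.3.5 then states that Confirmed and Probable events "will be summarized in the AEs of special interest table", and that all suspected cases are listed by subject. Protocol 6.10.11 notes that "DKA is a serious, acute complication of diabetes and can be life-threatening"; it gives no alternative case definition.

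**The concern.** When ketones and acidosis have been measured, whether the patient then improved says nothing further about whether ketoacidosis occurred. Making improvement part of the definition lets a documented case fail on its outcome, and the cases that can fail are those with the worst course. Table 7 has no residual category and no rule for death or failed treatment.

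The plan treats response differently for severe hypoglycemia. In SAP 9.3.3.2 and Protocol 6.10.10, recovery after glucose stands in for a missing measurement. In Table 7 it is demanded on top of the measurements.

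At stake is the adjudicated DKA line in the special-interest table, which is reported by arm. If the drug raises DKA risk and such a case occurs on drug, that line would understate the difference.

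**Working it through.** The plan states no figure to reproduce; this is a check of definitions.

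**Step 1: one case against every criterion.** Take severe symptoms, ketonemia, measured acidosis, and death before treatment or with no response.

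| Category | Why the case fails |
|---|---|
| Confirmed | no response |
| Probable, first branch | no response |
| Probable, second branch | no response; acidosis is present |
| Possible, three branches | symptoms must be mild to moderate, mild, or absent |
| Unlikely | symptoms must be mild or absent |
| Indeterminate | symptoms must be mild to moderate and ketosis unmeasured |

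**Step 2: all combinations.** Table 7 was coded literally over 4 symptom grades (none, mild, moderate, severe) × 5 ketone levels (not measured, negative or small, moderate, 4+, 5+) × acidosis yes/no = 40 cells. The cells are logical combinations, not frequencies.

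- Neither response nor self-resolution, severe symptoms: 10 of 10 cells fit no category.
- Neither response nor self-resolution, moderate or severe symptoms: 20 of 20 fit no category.
- With response, moderate or severe symptoms: 0 of 20 are unclassified.
- Neither response nor self-resolution, all 40 cells: 0 qualify as Confirmed or Probable. Those that fit anything have mild or no symptoms and fall under Possible or Unlikely.

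The response clause alone therefore separates 20 classified cells from 20 unclassified ones.

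**Step 3: which count applies.** SAP 9.3.3.5 counts Confirmed and Probable, and SAP 2.1 uses the same pair. SAP 9.3.3 instead names confirmed and possible events for the same table. The case in Step 1 is missed under either rule.

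**Step 4: scale, on assumed rates.** The documents give no DKA rate, so 1 to 4 per 1,000 patient-years is assumed purely for illustration. Withdrawal of 6.5% a year gives a hazard λ = −ln(0.935) = 0.0672. For potential follow-up uniform on (a, b) years, mean follow-up = (1/λ)[1 − (0.935^a − 0.935^b)/(λ(b − a))].

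- (2, 3) years: (1/0.0672)[1 − (0.8742 − 0.8174)/0.0672] ≈ 2.30 years; × 1,100 bexagliflozin subjects ≈ 2,530 patient-years; 2.5 to 10 events; one case is about 10% to 40% of the arm's count.
- (1, 3) years, the minimum and maximum in Protocol 9.2: (1/0.0672)[1 − (0.9350 − 0.8174)/(2 × 0.0672)] ≈ 1.86 years; ≈ 2,050 patient-years; 2.05 to 8.2 events; one case is about 12% to 49%.

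These shares show what one omitted case would weigh. They say nothing about how likely one is.

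**The case against.** Several points on the other side stand.

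- A reader might infer that any fatal ketoacidosis is lost. Table 7 does not say so: it asks that the episode respond, not that the patient survive. A subject whose ketoacidosis improves on fluids and who later dies still meets Confirmed. Nor is insulin always required; it is conditional in Confirmed and in the first Probable branch, and an alternative in the second.
- A reader might infer that the case disappears from the report. It would not. It stays in the by-subject listing of suspected DKA and in the serious TEAE and death outputs of SAP 9.3.2. An event coded to another acidosis term might also appear under acid-base disorders, although SAP 9.3.3 exempts DKA itself from preferred-term identification, so this is unclear.
- The adjudicator must choose one of five categories and might place such a case in Confirmed despite the text. That is possible, but the SAP gives no rule for it, and an unwritten override is what prespecified definitions are meant to avoid.
- A reader might infer a demonstrated bias in the comparison between arms. The documents do not support that. DKA is a descriptive summary with no planned test, and nothing shows that such a case will occur.

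It could also be argued that the response clause is only descriptive. The first Probable branch tells against this: without response as a requirement, moderate or severe symptoms alone would make a Probable DKA.

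**Conclusion.** The definitional gap is real and narrow. As written, a severe, biochemically documented ketoacidosis without response, or with death before response could be seen, meets none of the five definitions and would be omitted from the adjudicated DKA count. This follows from the text of Table 7 and needs no numerical assumption. Its effect on the reported results is conditional on such a case arising. There may be none; if there is one, it could be a sizeable part of a small count, but the percentages in Step 4 rest on assumed rates. The point merits correction because the wording misplaces a proven case and the remedy is nearly free.

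**What to change.** In Table 7:

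1. Confirmed DKA: make response supportive, so that symptoms plus ketonuria or ketonemia plus biochemical acidosis suffice.
2. Probable DKA, second branch only: accept a fatal course, a refractory course or an unassessable response in place of response. This branch already requires moderate or large ketonuria and/or ketonemia.
3. Leave the first Probable branch unchanged. It requires neither ketones nor acidosis. The presentations listed in Protocol 6.10.11, such as difficulty breathing, vomiting and lethargy, are non-specific. With up to 400 heart-failure subjects and 79 deaths projected over 2 years (SAP 3.7), extending the exception to this branch could turn suspected episodes ending in death from other causes into Probable DKA.

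On the Step 2 grid, of the 20 moderate or severe cells without response, 6 become Confirmed (2 symptom grades × 3 positive ketone levels, acidosis present) and 6 become Probable (the same without acidosis). The other 8 have ketones not measured, or negative or small, and stay outside the count; the adjudication form should say where they go.

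Before unblinding, have the blinded adjudicator apply the revised wording to any suspected case with a fatal or unresolved outcome. Reconcile SAP 9.3.3 with SAP 2.1 and 9.3.3.5 on which categories are counted.

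The cost is an edit to the SAP and adjudication form and a blinded re-read of any affected cases, with no new data collection. Specificity falls slightly, since Confirmed sets no minimum ketone level, and the DKA count may be slightly higher.

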9.4. LABORATORY EVALUATIONS

Laboratory tests will include hematology panel, chemistry panel, serum lipids, and urinalysis testing. Hematology, chemistry, serum lipids, and urinalysis will be performed at the following time points: at the screening visit (Week -2 to -5), at week 0, 6, 12, 24, 36, 48 from screening to week 48, at every 24 weeks after week 48 to end of study, at end of treatment visit and follow up (4 weeks after end of treatment visit) visit. Renal functional testing by UACR will be determined at screening visit (Week -2 to -5), at week 0, 24, 36, 48 from screening to week 48, at every 24 weeks after week 48 to end of study and end of treatment visit. The study staff will contact each subject prior to a scheduled clinic visit to confirm the time of the visit and to remind the subject of proper fasting practice. A subject must be queried to assess compliance with an approximately 10-hour fast prior to blood draw to ensure the FPG and triglycerides values can be accurately determined. If a subject has not fasted for approximately 10 hours, the subject must return as soon as can be arranged (within 1 week) to provide a specimen after proper fasting. A list of laboratory tests is included in Table 8.

Low density lipoprotein cholesterol (LDL-C) will be calculated by the Friedewald equation. Direct LDL-C will be determined in subjects whose triglycerides are $> 350 \text{ mg dL}^{-1}$ at the screening visit. All subsequent LDL-C of these subjects will be determined by direct LDL-C measurements only. The following algorithm will be used to obtain LDL-C values for the analyses:

1. Select subjects (based on the SI unit) who have screening triglycerides $>3.4 \text{ mM}$ or $>350 \text{ mg dL}^{-1}$ based on the laboratory value reported
2. Take the LDL - direct measurement values only, throughout the study visits for those subjects
3. If screening triglycerides > 350 and no direct LDL-C values have been determined, take the calculated.

Among those subjects who have screening triglycerides >350 and have both calculated and direct LDL values, only take the direct LDL.

Urinalysis microscopy will be conducted if the subject has a positive result on the leukocyte esterase or nitrite dipstick tests to clarify the significance of the finding. Results of glucose measurement in the urinalysis must be suppressed from the

laboratory reports so the sponsor, investigators, study coordinators, pharmacists, study subjects, and the adjudication committee members will remain blinded to the dosing assignment.

The baseline value for all laboratory tests will be the latest value obtained on or prior to Day 1. Change from baseline for all continuous parameters will be calculated as the post-baseline value minus the baseline value. All continuous variables will be summarized by number of subjects [n], mean, SD, Q1, median, Q3, minimum and maximum and categorical variables will be summarized by frequency and percentage.

Observed values (in SI units) and change from baseline over time will be summarized by treatment arm. Laboratory data will be classified as low, normal, or high relative to the parameter's reference range. Laboratory abnormalities for each treatment will also be summarized with shift tables for selected parameters.

For hematology, chemistry, and serum lipids, columns will be included for normal ranges and individual abnormal laboratory values will be flagged and clinical significance will be indicated.

Urine albumin/creatinine ratio (UACR) will be summarized and analyzed separately. Descriptive statistics for geometric mean, geometric coefficient of variation (gCV), median, Q1, Q3, minimum, and maximum of UACR values will be presented at screening, baseline, and all post-baseline scheduled visits for all subjects and for baseline macroalbuminuria subjects ($>300 \text{ mg g}^{-1}$). UACR data is left-skewed and will be natural log transformed first. Change in log transformed UACR from baseline to week 24 will be analyzed by ANCOVA model. The fixed effect will include region, baseline HbA_{1c} level as continuous variable, region, baseline eGFR categories (<60 or $\geq 60 \text{ mL min}^{-1} \text{ per } 1.73 \text{ m}^2$), baseline BMI ($<$ or $\geq 25 \text{ kg m}^{-2}$), history of heart failure (yes or no), insulin use or not, and treatment. The log transformed baseline values will be used as covariate. Analysis will be repeated for baseline macroalbuminuria subjects. LS means for each treatment will be estimated at week 24. The adjusted geometric mean ratio of relative change from baseline in UACR (the ratio of the week 24 geometric mean and baseline geometric mean) and the corresponding two sided 95% CI by treatment arm will be calculated as the antilog of the LS mean and 95% CI of log transformed values, converted to percentage.

Biomarker evaluation is an exploratory study that will be analyzed and reported in a separate report. The biomarker results will not be included in the subject listing or summarized in the THR-1442-C-476 study report. Summary and shift table of hematology, summary of urinalysis, and analysis table of UACR will also be conducted for subjects who have been prescribed insulin or sulfonylurea to control their diabetes.

Table 8 List of Laboratory Tests

Test Name	Blood or urine Vol. (mL)	Shipment
Hematology¹	2 (blood)	Ambient
Hematocrit (Hct)	Mean corpuscular volume (MCV)	
Hemoglobin (Hgb)	Red cell distribution width (RDW)	
Mean corpuscular hemoglobin (MCH)		
Mean corpuscular hemoglobin concentration (MCHC)	Red blood cell (RBC) count	
Platelet count	White blood cell (WBC) count with differential	
Serum Chemistry and Electrolytes	5 (serum)	Ambient
Albumin (ALB)	Total protein	
Alanine aminotransferase (ALT)	Calcium (Ca)	
Aspartate aminotransferase (AST)	Magnesium	
Alkaline phosphatase (ALK)	Phosphorus	
Blood urea nitrogen (BUN)	Potassium (K)	
Glucose	Sodium (Na)	
Bicarbonate (HCO ₃)	Total bilirubin	
Creatinine	Direct bilirubin	
Chloride (Cl)	Uric acid	
Glycemic Control		Ambient
Fasting plasma glucose (FPG)	2 (plasma)	
Hemoglobin A _{1c} (HbA _{1c})	2 (blood)	
Serum Lipids^{1, 2}	6 (serum)	Ambient
Total cholesterol (TC)	Low-density lipoprotein cholesterol (LDL-C),	
High-density lipoprotein cholesterol (HDL-C)	calculated	
Triglycerides (TG)	LDL-C, direct	
Urinalysis³	10 (urine)	Ambient
Appearance	Nitrite	
Bilirubin	Occult blood	
Color	pH	
Glucose	Protein	
Ketones	Specific gravity	
Microscopic examination of sediment	Urobilinogen	
UACR	Leukocyte esterase	
Infectious Disease Testing	9 (serum)	Ambient
HBsAg	HCV	
HIV (Canada only)		
Urine pregnancy test (WOCBP)	2 (urine)	Local
Population PK Sampling	2 (plasma)	Frozen
Bexagliflozin plasma level		
Biomarker evaluation	5 (serum)	Ambient
NT-proBNP evaluation (select Group 2 subjects)	5 (serum)	Ambient

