6.7 Clinical Laboratory Tests

6.7.1 Laboratory Parameters

Subjects will be in a seated or supine position during blood collection. A schedule of each laboratory test is outlined in [Appendix 1](#). Clinical laboratory tests will include the following:

Table 1. List of Laboratory Tests

Test Name	Blood or urine Vol. (mL)	Shipment
Hematology¹	2 (blood)	Ambient
Hematocrit (Hct)	Mean corpuscular volume (MCV)	
Hemoglobin (Hgb)	Red cell distribution width (RDW)	
Mean corpuscular hemoglobin (MCH)	Red blood cell (RBC) count	
Mean corpuscular hemoglobin concentration (MCHC)	White blood cell (WBC) count with differential	
Platelet count		
Serum Chemistry and Electrolytes¹	5 (serum)	Ambient
Albumin (ALB)	Total protein	
Alanine aminotransferase (ALT)	Calcium (Ca)	
Aspartate aminotransferase (AST)	Magnesium	
Alkaline phosphatase (ALK)	Phosphorus	
Blood urea nitrogen (BUN)	Potassium (K)	
Glucose	Sodium (Na)	
Bicarbonate (HCO ₃)	Total bilirubin	
Creatinine	Direct bilirubin	
Chloride (Cl)	Uric acid	
Glycemic Control¹		Ambient
Fasting plasma glucose (FPG)	2 (plasma)	
Hemoglobin A1c (HbA1c)	2 (blood)	
Serum Lipids^{1,2}	6 (serum)	Ambient
Total cholesterol (TC)	Low-density lipoprotein cholesterol (LDL-C), calculated	
High-density lipoprotein cholesterol (HDL-C)	LDL-C, direct	
Triglycerides (TG)		
Urinalysis³	10 (urine)	Ambient
Appearance	Nitrite	
Bilirubin	Occult blood	
Color	pH	
Glucose	Protein	
Ketones	Specific gravity	
Microscopic examination of sediment	Urobilinogen	
UACR	Leukocyte esterase	
Infectious Disease Testing⁴	9 (serum)	Ambient
HBsAg	HCV	
HIV (Canada only)		
Urine pregnancy test (WOCBP)⁵	2 (urine)	Local
Population PK Sampling⁶	2 (plasma)	Frozen
Bexagliflozin plasma level		
Biomarker evaluation⁷	5 (serum)	Ambient
NT-proBNP evaluation (select Group 2 subjects)⁸	5 (serum)	Ambient

¹ Blood for clinical chemistry and hematology will be drawn after 10 h of fasting prior to breakfast (i.e. only water is allowed, no caloric intake).

² LDL-C will be calculated by the Friedewald equation. If triglycerides are > 400 mg/dL, the calculated LDL-C value is invalid by this equation and will be set as missing. Direct LDL-C will be determined in subjects whose baseline triglycerides are > 350 mg/dL. All subsequent LDL-C of these subjects will be

determined by the same direct LDL-C measurements only.

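### SAP 9.4 equates 3.4 mM with 350 mg/dL triglycerides, but 3.4 mM is about 301 mg/dL, so subjects between the two figures can lose valid calculated LDL-C

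*Combined protocol and SAP*

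**What the plan says.** SAP 9.4 (Laboratory Evaluations) sets out which LDL-C value enters the analysis.

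- **Step 1:** "Select subjects (based on the SI unit) who have screening triglycerides" above 3.4 mM or above 350 mg/dL, going by the reported laboratory value.
- **Step 2:** "Take the LDL - direct measurement values only, throughout the study visits for those subjects".
- **Step 3:** "If screening triglycerides > 350 and no direct LDL-C values have been determined, take the calculated". The 350 carries no unit.

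On who receives a direct measurement, Protocol 6.7.1, Table 1, footnote 2 says: "Direct LDL-C will be determined in subjects whose baseline triglycerides are > 350 mg/dL". Protocol Appendix 2 (footnote 2), SAP Table 4 (footnote 2) and the SAP 9.4 text just before the algorithm also give 350 mg/dL. The same Table 1 footnote limits the calculated value: "If triglycerides are > 400 mg/dL, the calculated LDL-C value is invalid by this equation and will be set as missing".

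On reporting, SAP 9.4 adds: "Observed values (in SI units) and change from baseline over time will be summarized by treatment arm".

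**The concern.** Step 1 presents 3.4 mM and 350 mg/dL as one threshold in two units. If they differ, the threshold that is programmed depends on the unit. The text points to the SI unit, and the laboratory summaries are in SI units, so 3.4 is the figure most likely to be coded.

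A cut-off that is too low in SI units pulls in subjects for whom no direct LDL-C is planned. Step 2 then bars their calculated values at every visit, although those values are valid below the 400 mg/dL limit. At stake is the completeness of the LDL-C summaries and changes from baseline, which would have a gap at one range of raised triglycerides.

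**Working it through.** **Inputs.** From SAP 9.4 step 1: 3.4 mM and 350 mg/dL. From Protocol Table 1, footnote 2: direct measurement above 350 mg/dL; calculated value invalid above 400 mg/dL. Assumed: 88.57 mg/dL per mmol/L for triglycerides, with a deliberately wide range of 85 to 92.

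**1. Do the plan's two figures agree?** Formula: mg/dL = mmol/L × factor.

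- 3.4 × 88.57 = 301.1 mg/dL
- Over the factor range: 3.4 × 85 = 289.0 and 3.4 × 92 = 312.8 mg/dL
- If 3.4 is a rounded value: 3.35 × 88.57 = 296.7 and 3.45 × 88.57 = 305.6 mg/dL
- Factor needed for the pair to match: 350 / 3.4 = 102.9

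The pair cannot be reproduced by any factor in the range or by rounding.

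**2. What is 350 mg/dL in SI units?** 350 / 88.57 = 3.95 mM (350 / 92 = 3.80 to 350 / 85 = 4.12 mM).

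**3. Which figure is out of line?** Every mg/dL statement of the direct-measurement trigger says 350. Only the 3.4 mM figure differs. It is close to a rounded conversion of 300 mg/dL (300 / 88.57 = 3.39 mM), but the documents do not say where it came from.

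**4. Trace of steps 1 to 3.** This applies 3.4 mM to SI results and reads the 350 in step 3 as mg/dL.

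| Screening triglycerides (mg/dL) | Selected in step 1? | Direct value exists | No direct value |
|---|---|---|---|
| up to about 301 | no | calculated | calculated |
| about 301 to 350 | yes | direct | **none: step 2 bars calculated, step 3 does not apply** |
| above 350, up to 400 | yes | direct | calculated (step 3) |
| above 400 | yes | direct | step 3 points to the calculated value, which Table 1 sets to missing while triglycerides exceed 400 |

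**5. Same trace with 3.95 mM in step 1.** Subjects at about 301 to 350 mg/dL are no longer selected and keep their calculated LDL-C. The other rows do not change.

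**The case against.** The best defence is that the SAP, read as a whole, makes 350 mg/dL the intended cut. The sentence before the algorithm, step 3 and the closing sentence of the algorithm all use 350, and step 1 refers to the reported laboratory value, which would allow 350 to be applied to results in mg/dL. A careful programmer might notice the slip. This stands in part: the loss depends on the SI figure being applied. It does not remove the defect. If the two conditions are joined as a logical OR, the lower one governs. If the cut follows the reporting unit, subjects with the same triglycerides are handled differently according to their laboratory's units.

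Nor does every subject in the band necessarily lack a direct value. Protocol Table 1, Protocol Appendix 2 and SAP Table 4 trigger direct measurement on baseline triglycerides, whereas SAP 9.4 uses screening. Lipids are drawn at both V1 and V3, so a subject in the band at screening who exceeds 350 mg/dL at V3 could have direct values. That objection is sound and limits the loss to band subjects without one.

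Two stronger readings are tempting, and the documents do not support them:

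- A reader might infer that LDL-C is lost for every subject without a direct measurement. Step 3 keeps the calculated value above 350, so the loss is confined to about 301 to 350 mg/dL.
- A reader might infer that step 3, having no upper limit, lets invalid calculated values in at later visits. Protocol Table 1 already sets calculated values to missing above 400 mg/dL, with no visit limit. What remains is a wording difference: Protocol Appendix 2 and SAP Table 4 tie that rule to screening.

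**Conclusion.** The mismatch is real: 3.4 mM is about 301 mg/dL, not 350 mg/dL, and no plausible conversion closes the gap. Applied on the SI unit as written, step 1 opens a band of about 49 mg/dL (350 − 301) in which subjects without a direct value lose valid calculated LDL-C from the summaries.

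This rests on the standard conversion factor, on the SI figure being the one programmed, and on the 350 in step 3 meaning mg/dL. The number of subjects affected cannot be given, because the documents contain no triglyceride distribution.

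The importance is small. LDL-C is not a listed efficacy or named safety endpoint and has no model or test. The selection value precedes randomization, so the rule treats both arms alike and does not by itself bias the comparison between them. SAP 6.1 also puts all available data in the subject listings. It is still worth correcting, because it is a wrong threshold in a rule that will be programmed directly.

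**What to change.** In SAP 9.4 step 1, replace 3.4 mM with 3.95 mM. In step 3, write the cut-off with its unit (350 mg/dL, 3.95 mM).

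While the text is open, reconcile the 400 mg/dL validity rule, which has no visit limit in Protocol Table 1 but is limited to screening in Protocol Appendix 2 and SAP Table 4.

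The cost is one number, one unit and one clarifying phrase. No new data and no change to study conduct are needed.
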